Researchers have used visual pedagogy to show a structured method and technique of tooth brushing by series of pictures. The pictures were placed in the bathroom or wherever tooth brushing was performed, and the visual pedagogy was proved to be a useful tool in helping children with special needs to improve their oral hygiene (Pilebro c., et al. 2005). Goyal S. et al. even showed that for mentally challenged individuals, manual toothbrushes reinforced with audio-visual instructions for brushing might be comparable to the use of powered toothbrushes (Goyal, S. et al. 2011).

However, to date there has been limited researches focused on the effectiveness of toothbrushing assisted with visual pedagogy to promote oral health among special care communities. Community-based studies are necessary to provide reliable evidence to support or refute the interventions. In the proposed study, standard tooth-brushing training, along with a package of structured social stories illustrating the tooth-brushing procedure, healthy diets, and dental visit will be provided to preschool children with special needs. We hypothesized that oral-health related behaviours will be modified among children who receive visual-pedagogy (social story) -assisted tooth-brushing training, and thereby, their oral health status will be improved after intervention.

Method

Trial design

This study will be designed as a block-randomised controlled parallel blind clinical trial. Duration of the study will be 24 months.

Recruitment

Participants will be recruited from the Special Child Care Centers and Special Schools of The Spastics Association of Hong Kong (SAHK). Children aged from 2-6 years old with special care conditions such as Prader-Willi syndrome, intellectual disability (ID), autistic spectrum disorders (ASD), cerebral palsy (CP), Down's syndrome (DS), attention deficit hyperactivity disorder (ADHD), delayed development, or learning disorders will be invited to participant in this study. Consent form and information sheet will be delivered to children meet the above requirement. Only children with informed consent signed by parents will be recruited.

Exclusion criteria

Children manifested with at least one of the following conditions will be excluded from this clinical trial:

- Severe visually impaired
- Severe hearing impaired
- Severe physical disabled (cannot hold a toothbrush)
- Requiring emergent dental treatment
- Use of antibiotic within 3 months

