- Dental prophylaxes in the last 6 months

Sample size calculation

The primary outcome is the development of new dental caries in the children over the 24-month study period. Based on the previous oral health promotion conducted among healthy preschool children in Hong Kong (Jiang M., 2013), the mean dmfs in control group and intervention groups are 0.3 (SD = 1.3), 0.2 (SD = 0.7), 0.4 (SD = 1.2). We assumed that the mean dmfs in control group and test group are 0.7 (SD = 1.0) and 0.3 (SD = 0.5). The program G* power 3.1.9.2 is used for sample size calculation: two-tail test, a =0.05, at a power of 95%. This give

a sample size target of 105 children per group. Considering 30% overestimation to allow for dropout in 2 years, totally 300 children will be invited, with 150 children per group.

Baseline information

Baseline information will consist of the following components:

- Clinical oral examination
- Tooth-brushing performance observation
- Questionnaire-based survey

Clinical oral examinations will be performed according to the following criteria: i) Caries status were assessed by the International Caries Detection and Assessment System(ICDAS); ii) Oral hygiene status by Simplified oral hygiene index of Greene and Vermilion (OHI-S); iii) gingival health status by Modified Gingival Index of Lobene (MGI). Dental examination will be performed at Special Child Care Centers by a pediatric dentist with a disposable mouth-mirror attached to an LED light. Tell- Show-Do (TSD) technique will be used to improve children's cooperation level. Tooth-brushing performance will be assessed by two observers. There will be 13 steps listed in the assessment form, steps which are performed by child or parent will be recorded respectively, as well as the total time for each tooth-brushing session. After dental examination and tooth-brushing assessment, a standard hands-on toothbrushing training will be provided immediately to each child and his/her parent. Oral health instruction will also be illustrated to the participants, reinforced by social stories or conventional leaflets. Questionnaires regarding children's oral health related behaviours, family demographic information and parents' oral health literacy assessment will be completed by parents, while questionnaires assessing children's developmental profile will be filled by staff in Special Child Care Centers.

Allocation

3

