Statistical Analysis Plan

Official Title:

Effectiveness of visual pedagogy-assisted tooth-brushing training among preschoolers with special needs for oral health promotion

Date: 2015.11.22

All the data will be analysed using IBM SPSS. Variables from the questionnaires will be analysed by t test for independent samples or its non-parametric equivalent for continuous data and Chi-square tests for categorical data. Descriptive statistics of cooperation with tooth brushing in each group will be determined and variations in cooperation with tooth-brushing and developmental level of special needs will be determined by Chi-square statistics. McNemar's test will be used to analyse whether children's oral-health related behaviours will be changed before and after intervention. Then regression analyses will be conducted to determine developmental factors associated with children's oral health status or cooperation in conducting tooth brushing, accounting for child's age and gender in the model. Variations in simplified oral hygiene index, modified gingival index, caries incidence, number of completed tooth brushing tasks and time taken to complete the overall task will be determined using repeated measures ANOVA (or Friedmann ANOVA for nonparametric data). Inter-group comparisons of the above outcome variables with respect to baseline will be determined using paired t-test (or Wilcoxon signed rank for nonparametric data). Intra-group comparisons of at baseline, 6-month, 12-month, and 24-month will be conducted using student's t-test (or Mann Whitney U test for nonparametric data). Magnitude of change will be derived through effect size calculation (mean change/ SD of baseline values) to provide an indication of clinical significance of the results. The significance levels will be set to be $P < 0.05$.

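### No between-arm caries comparison in the SAP adjusts for age or baseline caries; pre-specifying both would give a modest gain in precision at very little cost.

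*SAP*

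**What the plan says.** The Protocol, under Sample size calculation, states: "The primary outcome is the development of new dental caries in the children over the 24-month study period". Under Recruitment it admits "Children aged from 2-6 years old with special care conditions". Under Baseline information it has caries scored by ICDAS, and under Follow-up appointments the examination is repeated to the same criteria. Under Allocation, randomisation is concealed and blocked at school level. No stratification by age or by baseline caries is mentioned.

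For a set of outcomes that includes caries incidence, the SAP lists three kinds of test:

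- repeated measures ANOVA or Friedman;
- paired t-test or Wilcoxon signed rank against baseline;
- a two-sample test at each visit: "baseline, 6-month, 12-month, and 24-month will be conducted using student's t-test (or Mann Whitney U test for nonparametric data".

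None has a covariate. The regression that does have covariates is meant to find developmental factors related to oral health status or cooperation, "accounting for child's age and gender in the model". Baseline caries is not listed there. No analysis is named as primary.

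The SAP's labels also appear to be swapped. The paired tests are called inter-group, and the independent-samples tests are called intra-group. On either reading the arm comparison is unadjusted.

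**The concern.** Age and past caries are the two obvious candidates for explaining why some preschool children develop new caries and others do not. Both are available before randomisation, and the SAP itself treats age as relevant in its regression. Leaving them out of the arm comparison keeps their contribution in the residual variance, so the confidence interval is wider than it need be. Nothing stated in the design balances them either.

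Timing matters as well. Adjustment decided on after an imbalance has been seen is open to challenge; adjustment fixed in the SAP is not.

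**Working it through.** **Inputs from the Protocol (Sample size calculation).** "We assumed that the mean dmfs in control group and test group are 0.7 (SD = 1.0) and 0.3 (SD = 0.5"); "two-tail test, a =0.05, at a power of 95" per cent; "a sample size target of 105 children per group"; 150 per group after a 30% allowance for dropout.

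**Reproducing the plan's figure.**

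- Pooled SD = √((1.0² + 0.5²)/2) = 0.791.
- d = 0.4/0.791 = 0.506.
- n per group for 95% power, two-sided 5%: 102 by the normal approximation, 103 by the noncentral t, and exactly 105 with d rounded to 0.5.
- Dropout: 105/(1 − 0.30) = 150.

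The stated size is therefore that of an unadjusted two-sample comparison of means.

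**Effect of adjustment.** Let R be the multiple correlation of new caries with age and baseline caries within arms. The documents give no value, so R from 0.2 to 0.7 is an assumption, taken as equal in both arms. Children are assumed to be individually allocated, with 105 per group analysed.

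- Unadjusted SE = 0.791 × √(2/105) = 0.109; CI half-width = 1.96 × 0.109 = 0.214 dmfs.
- Adjusted SE = unadjusted SE × √(1 − R²).

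| R | Variance factor 1 − R² | SE | CI half-width (dmfs) | Power at 105 | n per group for 95% power (d = 0.5) |
|---|---|---|---|---|---|
| 0 | 1.00 | 0.109 | 0.214 | 95.4% | 105 |
| 0.2 | 0.96 | 0.107 | 0.210 | 96.1% | 101 |
| 0.3 | 0.91 | 0.104 | 0.204 | 96.9% | 96 |
| 0.5 | 0.75 | 0.094 | 0.185 | 98.8% | 79 |
| 0.7 | 0.51 | 0.078 | 0.153 | 99.9% | 54 |

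**If the outcome is more variable than planned.** The Protocol quotes SDs of 1.3, 0.7 and 1.2 from the earlier study in healthy preschoolers. Taking 1.3 and 0.7 with the same difference of 0.4:

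- Pooled SD = √((1.3² + 0.7²)/2) = 1.044.
- Unadjusted power = 78.9%.
- Adjusted power = 82.6% (R = 0.3), 89.1% (R = 0.5), 97.2% (R = 0.7).

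**The same loss seen as chance imbalance.**

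- The standardised arm difference in a baseline score has SE √(2/105) = 0.138, so it exceeds 0.2 SD in either direction with probability 0.147.
- At correlation 0.4, an imbalance of 0.2 SD moves the unadjusted estimate by 0.4 × 0.2/0.506 = 16% of the planned effect.
- At the 95% limit, 1.96 × 0.138 = 0.27 SD. The shift is then R × 0.791 × 0.27, or 0.04, 0.06, 0.11 and 0.15 dmfs for R = 0.2, 0.3, 0.5 and 0.7. These are 11%, 16%, 27% and 37% of the planned 0.4.

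**The case against.** The strongest case against is that this is an efficiency option for a valid test in a trial planned at 95% power. At R of 0.2–0.3 and the planned SDs, the gain is about 1 to 1.5 percentage points, and the documents offer no evidence on R. That stands, and it keeps the point modest.

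It can also be said that an increment already takes account of baseline. It subtracts the starting count, but it does not condition on the child's caries risk and it leaves age untouched. The gain from baseline caries may still be smaller than it would be for a raw 24-month score.

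Four stronger readings are tempting, and the documents do not support them:

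- **The unadjusted result is biased.** Under individual randomisation it is not biased in expectation, and its standard error already allows for covariate imbalance.
- **Lost power and chance imbalance are two separate harms.** They are one loss described in two ways and should not be added.
- **A covariate-adjusted count model would bring large power gains.** In simulations under assumed dispersion and baseline distributions, adjusted quasi-Poisson rejected a true null in about 5–8% of runs, so part of its apparent gain is false positives. Scenarios that add prognostic variance on top of the dispersion also exceed the planned SDs. A linear ANCOVA with robust errors held about 5% and gained only about 0.5 to 4.5 points over the t-test. Making a rate ratio the primary measure would also depart from the mean difference on which the trial was sized.
- **The SAP's regression excludes allocation.** The SAP does not list all its terms. What can be said is that its stated purpose is not to estimate the effect of allocation.

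**Conclusion.** The point holds as a matter of precision. Neither age nor baseline caries enters any between-arm caries comparison in the SAP, although both are available and no stratification on either is stated. At the planned SDs the benefit is mainly a narrower interval: the variance of the difference falls by 4–9% at R of 0.2–0.3 and by 25% at R of 0.5. The gain in power becomes material only if the outcome is more variable than planned, as with SDs of 1.3 and 0.7.

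All of these figures rest on an assumed R and on individual allocation. The Protocol's wording on school-level blocking could mean children within schools or whole schools. If whole schools were allocated, chance imbalance would be larger than shown and clustering would have to be handled as well. The more basic gap is that no primary between-arm test is named, and one sentence in the SAP can close both.

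**What to change.** Name one primary between-arm analysis of new caries at 24 months: a linear model (ANCOVA) with heteroscedasticity-robust standard errors. Its terms should be arm, age, baseline caries (for example log(1 + count)), and school as the randomisation factor. If schools rather than children were allocated, use clustered inference instead of fixed school terms, because arm would then be confounded with school; the Protocol should say which applies.

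Report the adjusted mean difference with its 95% CI, which matches the sizing. Keep the unadjusted test, and optionally a log-link count model, as sensitivity analyses. Correct the inter-group and intra-group labels in the same edit.

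The cost is a sentence or two in the SAP and a few degrees of freedom, with no new data and no more children.

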Concealed block randomization at school levels will be used to allocate subjects into 2 group. The randomised sequence will be generated by an investigator who do not participate in the outreach service. The allocation sequence will be sealed in an envelope, and opened at the Special Child Care Centres by an assistant, who will also be responsible for delivering the materials to children and their parents. Hence, children (participant) and investigators (outcome assessor) will not know the randomised sequence. After a standard tooth-brushing training and oral health instruction, Group 1 will be set up as a positive control, receiving standard oral-health education leaflets issued by the local government, while Group 2 will act as test group, receiving social stories developed and validated by the investigators.

Follow-up appointments

Commercially available toothbrushes and fluoridated toothpaste will be delivered to each child and renewed at every three months. Meanwhile, the old toothbrush and remaining toothpaste will be returned, and toothpaste usage and toothbrush wear will be monitored. Follow-up assessments will be performed at 6-month, 12-month, 24-month. Education materials about "healthy diets" will be emphasized at 6-month follow-up, and dental-visit related education materials will be emphasized at 12-month follow-up. Tooth-brushing training was reinforced at each follow-up appointment. Education material about tooth brushing, healthy diets and dental visit will be illustrated to children and their parents, and parents will be encouraged to read those materials to their children in their daily lives. Oral examination and tooth-brushing assessment in follow-up appointment will be performed using the same methods and criteria as baseline; all parents or primary caregivers will complete a set of questionnaires on their attitudes towards the interventions and their children's oral-health related behaviours.

Significance

The present study will provide scientific evidence of effective oral health care for children with special needs. Meanwhile, the interventions adopted in the control group and test group have potential benefits to encourage the children with special needs to take care of themselves by learning tooth brushing independently at an early age status, supporting their relatively independent life in the future.

References

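### Where a t-test compares caries between arms, the SAP should name Welch's form: the pooled standard error is off if the assumed effect is real and the arms retain unequal numbers

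*SAP*

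**What the plan says.** The protocol's sample size section defines the endpoint: "The primary outcome is the development of new dental caries in the children over the 24-month study period". It assumes that the "mean dmfs in control group and test group are 0.7 (SD = 1.0) and 0.3 (SD = 0.5"), and sets "two-tail test, a =0.05, at a power of 95"%. This leads to "a sample size target of 105 children per group". The allowance for loss is a single figure, "Considering 30% overestimation to allow for dropout in 2 years", giving "totally 300 children will be invited, with 150 children per group".

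The SAP gives Student's t-test as the parametric choice for comparisons at baseline and the three follow-up visits, with the rank test as its alternative: "will be conducted using student's t-test (or Mann Whitney U test for nonparametric data"). That sentence is labelled as intra-group, while paired tests are assigned to inter-group comparisons. The two labels appear to be swapped, so I read the sentence as the between-arm comparison. The SAP names no unequal-variance form and no variance check. It also lists caries incidence under repeated measures ANOVA or its rank equivalent, does not say which analysis is primary, and mentions no confidence interval.

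**The concern.** Student's t-test, as usually understood, estimates one common variance. The trial's own planning figures put the variances at 1.0 and 0.25. When the arms are the same size, the pooled and separate-variance standard errors coincide and the assumption costs nothing. When they differ, the pooled variance leans towards the larger arm. If the control arm, with the larger spread, ends up smaller, the standard error is too small and an interval for the mean difference is too narrow. If the control arm ends up larger, the reverse holds.

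The plan allows for about 30% loss over two years and contains nothing that would make that loss equal by arm. What is at stake is the stated precision of the 24-month caries difference, in the scenario for which the trial is powered.

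**Working it through.** **Inputs.** Means 0.7 and 0.3, SDs 1.0 and 0.5, two-sided 5%, 95% power, 105 per group, 30% loss, 150 per group (protocol, sample size section). The completer splits below are my assumptions, because the documents give no dropout by arm.

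**The plan's own figure.** Pooled SD = √((1.0² + 0.5²)/2) = 0.791, and d = 0.4/0.791 = 0.506. The noncentral t calculation gives 103 per group at d = 0.506 and exactly 105 at d rounded to 0.5. Then 105/(1 − 0.30) = 150 per group, 300 in total. The stated numbers reproduce.

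**Standard errors**, with n₁ control and n₂ test completers:

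- Pooled variance: s² = [(n₁ − 1)·1.0 + (n₂ − 1)·0.25]/(n₁ + n₂ − 2)
- Pooled SE = √[s²(1/n₁ + 1/n₂)]
- True SE = √[1.0/n₁ + 0.25/n₂]

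Example at 90/120: s² = (89 + 29.75)/208 = 0.571. Pooled SE = √[0.571 × (1/90 + 1/120)] = 0.1054. True SE = √[1/90 + 0.25/120] = 0.1149. The ratio is 0.917, so the pooled SE is about 8% too small.

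**Coverage** of a nominal 95% interval was simulated with 40,000 runs per split. Control values were negative binomial (mean 0.7, variance 1.0). Test values were 0, 1 or 2 with probabilities 0.72, 0.26 and 0.02 (mean 0.3, variance 0.25). Repeat runs agree to within about 0.4 points.

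| Control/test completers | Pooled SE / true SE | Student coverage | Welch coverage |
|---|---|---|---|
| 105/105 | 1.00 | about 94.5% | about 94.6% |
| 98/112 | 0.961 | about 93.7% | about 94.7% |
| 90/120 | 0.917 | about 92.6% | about 94.5% |
| 120/90 | 1.09 | about 96.4% | about 94.9% |

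From 150 per arm, 98/112 means losing 52 and 38 children (35% and 25%), and 90/120 means losing 60 and 30 (40% and 20%).

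**P value under no effect.** With both arms drawn from the same negative binomial distribution (mean 0.7, variance 1.0), Student's test rejected in 4.9% to 5.0% of runs at 105/105, 95/115, 115/95, 90/120, 120/90, 105/150 and 150/105. The error rate moves only if the SDs differ while the means are equal. With normal data and SDs of 1.0 and 0.5, it was 7.2% at 90/120 and 3.3% at 120/90.

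**P value at the assumed effect.** With an observed difference of 0.4 at 90/120, Student gives P = 0.00019 and Welch P = 0.00069.

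**The case against.** The strongest reply is that the plan as written has no problem. It has equal arms and one dropout figure, and at 105/105 the two tests agree (interval half-widths 0.215 and 0.216). Both arms receive the same training, brushes and toothpaste, so a large difference in loss is conjecture. This stands as a limit on size. It does not show that retention will be equal, and the choice of test need not depend on a pattern unknown when the SAP is written.

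A reader might infer that the primary P value is invalid. The documents do not support that. The SDs of 1.0 and 0.5 are assumed together with different means, that is, under an effect. The 5% error rate is a property under no effect, and it holds there if the arms share one distribution. Unequal spread with equal means is not assumed anywhere, and it would be unusual for a count whose spread grows with its mean.

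A reader might also infer that a planned confidence interval is wrong. The SAP plans none, so the interval matters as something to add.

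Three further points stand in part. The planned dmfs has an SD above its mean in both arms, so caries may be sent to the Mann-Whitney test. But the SAP gives no rule for that choice, so the t-test remains a named route, and the rank test gives no interval for the mean difference on which the trial is sized. The SAP does not use the words equal variance; that is the usual meaning of the name. And the between-arm reading relies on treating the inter- and intra-group labels as swapped.

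**Conclusion.** The point holds in a limited, conditional form. The SAP names a test that normally pools variances, while the protocol plans on variances that differ fourfold. There is no harm with equal completers, and no harm to the P value if the intervention has no effect and the arms share one distribution. If the assumed effect is real and retention is unequal, the pooled standard error is off by about 4% to 9% across the assumed splits, and coverage is about 92.6% to 96.4% against about 95% for Welch. The direction depends on which arm loses more children.

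It would be tempting to conclude that the trial's result would change or that the sample size is wrong. Neither follows: at the assumed effect both tests give P below 0.001 in the splits examined, and the 105 and 150 per group reproduce. This is a free improvement to the precision statement, and it rests on the plan's SDs and on completer splits that I have assumed.

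**What to change.** In the SAP, where the between-arm caries comparison uses a t-test, name Welch's form (the SPSS output line for equal variances not assumed) and state that no preliminary variance test will decide between the two. Report the 24-month mean difference in caries with its Welch 95% confidence interval. The documents show unequal spread only for dmfs, so they do not require the change for other outcomes.

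The cost is a few words and one added interval. The planned sample size does not change, and with equal arms the result is practically the same. Naming the form in advance also removes a later choice between two printed lines.

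This does not deal with clustering. The protocol's allocation section says "Concealed block randomization at school levels will be used to allocate subjects into 2 group". The wording leaves open whether schools or children are the unit. If schools are, a Welch interval that ignores this would not have 95% coverage either, and the analysis needs separate handling.

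### McNemar's test and mean change over baseline SD measure change over time, not the difference between arms; keep them as per-arm description and add baseline-adjusted between-arm estimates with 95% CIs

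*SAP*

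**What the plan says.** The SAP is a single paragraph. On behaviours it states: "McNemar's test will be used to analyse whether children's oral-health related behaviours will be changed before and after intervention". It does not say whether the test is run in each arm or on both arms pooled. On size of effect it states: "Magnitude of change will be derived through effect size calculation (mean change/ SD of baseline values"), and it presents this ratio as the indication of clinical significance.

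The SAP also lists tests that can compare arms. For questionnaire items: "Variables from the questionnaires will be analysed by t test for independent samples", with chi-square for categorical items. For the clinical and brushing outcomes it gives repeated measures ANOVA without naming a group factor, and then two sentences whose labels and tests do not match:

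- "Inter-group comparisons of the above outcome variables with respect to baseline will be determined using paired t-test"
- "Intra-group comparisons of at baseline, 6-month, 12-month, and 24-month will be conducted using student's t-test"

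The regression looks for developmental factors, with age and gender as covariates. No arm term or baseline outcome is stated. No between-arm effect estimate or confidence interval is specified anywhere.

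The Protocol (Baseline information) says that "a standard hands-on toothbrushing training will be provided immediately to each child and his/her parent". Under Follow-up appointments, "Commercially available toothbrushes and fluoridated toothpaste will be delivered to each child and renewed at every three months", and brushing training is repeated at every visit without restriction by arm. Under Allocation, Group 1 is a positive control given government leaflets and Group 2 receives social stories. The Background hypothesis is that "oral-health related behaviours will be modified among children who receive visual-pedagogy (social story) -assisted tooth-brushing training", with no mention of the leaflet arm.

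**The concern.** The trial asks whether social stories add anything to training that everyone receives. A before/after measure combines any effect of the stories with the effects of shared training, fluoride toothpaste, growing older and repeated assessment. It can be large when leaflets and stories work equally well.

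Two misreadings follow.

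- The hypothesis is worded as change among children given social stories, so a significant McNemar result in that arm would seem to confirm it even if the leaflet arm changed just as much.
- If McNemar is run per arm, significance in one arm only can be taken as a difference between arms.

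Baseline values already collected could also sharpen the arm comparison, but no planned arm contrast is stated to use them. The point concerns outcomes measured at baseline: behaviours, OHI-S, MGI, brushing steps and brushing time. It does not concern caries incidence, which has no baseline value of its own.

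**Working it through.** **1. The plan's own figure.** The Protocol (Sample size calculation) assumes mean dmfs of 0.7 (SD 1.0) and 0.3 (SD 0.5), two-sided alpha 0.05 and power 95%.

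- Pooled SD = sqrt((1.0² + 0.5²)/2) = 0.791, so d = 0.4/0.791 = 0.506.
- The normal formula gives 102 per arm and the noncentral t gives 103. With d rounded to 0.50, the t calculation gives exactly 105.
- 105/(1 − 0.30) = 150 per arm.

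The stated size is reproduced, and it is the size for a between-arm comparison. I use 105 independent children per arm below.

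**2. Planned effect size when the arms are identical.** Set the baseline SD to 1 and let both arms gain 0.5 SD. Mean change / baseline SD = 0.5/1 = 0.50 in each arm, and the arm difference is 0.50 − 0.50 = 0. In 20,000 simulated trials the mean planned effect size was 0.50 in each arm. The between-arm t-test rejected in 4.8–5.4% and ANCOVA in 4.5–5.3%.

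**3. McNemar when the arms are identical.** The documents give no behaviour rates, so these are assumptions. Gain and loss are percentages of all children. The test is exact and two-sided at p < 0.05. With p the per-arm rate of significance, exactly one of two identical arms is significant with probability 2p(1 − p).

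| Gain/loss | Per arm, n = 105 | Pooled, n = 210 | Exactly one arm |
|---|---|---|---|
| 20/5% | 0.856 | 0.994 | 2 × 0.856 × 0.144 = 0.246 |
| 15/5% | 0.568 | 0.893 | 2 × 0.568 × 0.432 = 0.491 |
| 10/5% | 0.189 | 0.393 | 2 × 0.189 × 0.811 = 0.307 |

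The per-arm and pooled columns are correct detection of a common change, not error rates. The last column is the share of trials open to misreading as an arm effect. A separate simulation with other assumed rates (30/10, 25/10 and 20/10%, continuity-corrected McNemar) gave 19%, 42% and 48% for exactly one arm.

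**4. Between-arm tests on the same data.** Simulation with 10,000 runs, baseline prevalence 40% (assumed), no clustering. With identical arms at the three rates in step 3, follow-up chi-square rejects in 4.7%, 4.6% and 4.9%, and logistic regression on arm and baseline behaviour in 4.8%, 4.7% and 4.8%. Both are valid.

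Now let the test arm do better by 15 points at follow-up. In the first row, for example, the control arm ends at 40 − 5 + 20 = 55% and the test arm at 40 − 5 + 35 = 70%.

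| Control gain/loss | Test gain/loss | Chi-square power | Baseline-adjusted power |
|---|---|---|---|
| 20/5% | 35/5% | 61.5% | 69.8% |
| 15/5% | 30/5% | 59.5% | 71.7% |
| 10/5% | 25/5% | 57.5% | 76.6% |
| 25/10% | 40/10% | 62.5% | 63.5% |
| 30/20% | 40/15% | 59.9% | 60.1% |

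The gain depends on how well behaviour tracks from baseline. In the last row, half of the control children who start with the behaviour lose it (20 of 40), and there is no gain.

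**5. Precision for continuous outcomes.** The 95% CI half-width for the arm difference is 1.96 × sqrt(2/105) = 0.271 SD unadjusted. ANCOVA multiplies it by sqrt(1 − r²), where r is the assumed baseline/follow-up correlation:

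- r = 0.3: 0.258 SD (variance cut 9%)
- r = 0.5: 0.234 SD (25%)
- r = 0.7: 0.193 SD (49%)

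**The case against.** The strongest reply is that the SAP already has valid between-arm tests and never says that an arm conclusion will be drawn from McNemar or from the effect-size ratio. On that reading both are harmless descriptions, and the one-arm-only figures matter only if someone runs McNemar per arm and then misreads it. The hypothesis can also be read as comparative, since the trial is randomised, controlled and sized on control against test means. If the repeated measures ANOVA carries a group factor, its group-by-time term already uses baseline. Against a change-score contrast, with half-width 1.96 × sqrt((2/105) × 2(1 − r)), ANCOVA gains less at high correlation: 0.193 against 0.210 SD at r = 0.7, and 0.234 against 0.271 SD at r = 0.5.

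Much of this stands. Inference between arms is not invalid, provided the swapped labels are read as a slip. The misreading is a risk rather than a stated plan, and the power gain rests on assumed tracking. It is also fair that the missing estimate and interval affect caries incidence too.

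Three things remain. The SAP itself ties the uncontrolled ratio to clinical significance. The group factor in the ANOVA is not stated. No between-arm estimate or interval is specified. A comparative reading of the hypothesis strengthens the case for a comparative estimate.

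**Conclusion.** The concern holds. The planned index of clinical significance and the planned test of behaviour change cannot separate social stories from leaflets, because both arms receive the same training and supplies. An index of 0.50 in each arm is compatible with an arm difference of 0. Under the assumed rates, per-arm McNemar splits two identical arms in 25% to 49% of trials.

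Baseline adjustment does not improve false-positive control, which is already about 5%. It can add roughly 8 to 19 points of power for behaviours that track strongly, and close to nothing otherwise. For continuous outcomes it narrows the interval from 0.27 SD to between 0.26 and 0.19 SD.

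Prevalence, gain and loss rates, correlations and the 15-point effect are assumptions. All figures treat children as independent. If whole schools were allocated, the intervals would be wider; the documents give neither an intraclass correlation nor a number of schools. This should be changed, but it does not invalidate the trial.

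**What to change.** 1. Keep McNemar's test and mean change / baseline SD as within-arm description, reported separately by arm, and state that no conclusion about arms is drawn from them.
2. Correct the inter-group and intra-group labels so that paired tests are within arm and unpaired tests between arms. State whether the repeated measures ANOVA has a group factor.
3. For each outcome measured at baseline, report a between-arm estimate with 95% CI adjusted for its baseline value: ANCOVA or a mixed model for continuous outcomes, logistic regression on arm and baseline behaviour for behaviours. Say at which visit it is read, and whether it replaces the unadjusted visit-wise tests or takes precedence over them.
4. Express clinical significance of continuous outcomes as the adjusted between-arm difference divided by the pooled baseline SD.
5. Clarify whether block randomisation at school level means that schools were allocated whole or that children were randomised within schools. Compute the intervals accordingly, with a small-sample correction if few schools were allocated whole.

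The cost is SAP wording and one adjusted model per outcome that has a baseline value. The data are already collected, and this change does not itself call for a new sample size.
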